8.2.5.4. Abnormal Laboratory Values

Not every laboratory abnormality qualifies as an AE. A laboratory test result must be reported as an AE if it meets any of the following criteria:

- Accompanied by clinical symptoms
- Results in a change in study treatment (e.g., dosage modification, treatment interruption, or treatment discontinuation)
- Results in a medical intervention (e.g., potassium supplementation for hypokalemia) or a change in concomitant therapy
- Results in more frequent follow-up assessments or further diagnostic investigation
- Clinically significant in the Investigator's judgment

It is the Investigator's responsibility to review all laboratory findings. Medical and scientific judgment should be exercised in deciding whether an isolated laboratory abnormality should be classified as an AE.

If a clinically significant laboratory abnormality is a sign of a disease or syndrome (e.g., increased alkaline phosphatase (ALP) and bilirubin at $5 \times$ Upper Limit of Normal [ULN] associated with cholestasis), only the diagnosis (i.e., cholestasis) should be recorded on the Adverse Event CRF.

If a clinically significant laboratory abnormality is not a sign of a disease or syndrome, the abnormality itself should be recorded on the Adverse Event CRF, along with a descriptor indicating if the test result is above or below the normal range (e.g., "elevated potassium," as opposed to "abnormal potassium"). If the laboratory abnormality can be characterized by a precise clinical term per standard definitions, the clinical term should be recorded as the AE. For example, an elevated serum potassium level of 7.0 mEq/L should be recorded as "hyperkalemia."

Observations of the same clinically significant laboratory abnormality from visit to visit should not be repeatedly recorded on the Adverse Event CRF unless the etiology changes. The initial severity of the event should be recorded, and the severity or seriousness should be updated as described in [Section 8.2.5.3](#).

8.2.5.5. Abnormal Vital Sign Values

Not every vital sign abnormality qualifies as an AE. A vital sign result must be reported as an AE if it meets any of the following criteria:

- Accompanied by clinical symptoms
- Results in a change in study treatment (e.g., dosage modification, treatment interruption, or treatment discontinuation)
- Results in a medical intervention or a change in concomitant therapy
- Clinically significant in the Investigator's judgment

It is the Investigator's responsibility to review all vital sign findings. Medical and scientific judgment should be exercised in deciding whether an isolated vital sign abnormality should be classified as an AE.

If a clinically significant vital sign abnormality is a sign of a disease or syndrome (e.g., high blood pressure), only the diagnosis (i.e., hypertension) should be recorded on the Adverse Event CRF.

Observations of the same clinically significant vital sign abnormality from visit to visit should not be repeatedly recorded on the Adverse Event CRF unless the etiology changes. The initial severity of the event should be recorded, and the severity or seriousness should be updated as described in [Section 8.2.5.3](#).

8.2.5.6. Abnormal Liver Function Tests

Abnormal values in aspartate transaminase (AST) and/or alanine transaminase (ALT) levels concurrent with abnormal elevations in total bilirubin level that meet the criteria outlined below in the absence of other causes of liver injury are considered potential cases of drug-induced liver injury (potential Hy's Law cases) and should always be considered important medical events.

The threshold of laboratory abnormalities for a potential case of drug-induced liver injury depends on the subject's individual baseline values and underlying conditions. Subjects who present with the following laboratory abnormalities should be evaluated further to definitively determine the etiology of the abnormal laboratory values:

- Subjects with AST or ALT and total bilirubin baseline values within the normal range who subsequently present with AST or ALT values $> 3 \times$ ULN concurrent with a total bilirubin value $> 2 \times$ ULN with no evidence of hemolysis and an ALP value $\leq 2 \times$ ULN or not available.
- For subjects with preexisting ALT OR AST OR total bilirubin values above the ULN, the following threshold values should be used in the definition mentioned above:

- For subjects with preexisting AST or ALT baseline values above the normal range, AST or ALT value \geq 2 times the baseline values and $\geq 3 \times$ ULN, or $\geq 8 \times$ ULN (whichever is smaller).
- Concurrent with
 - For subjects with preexisting values of total bilirubin above the normal range: Total bilirubin increased from baseline by an amount of $\geq 1 \times$ ULN or if the value reaches $\geq 3 \times$ ULN (whichever is smaller).

The subject should return to the investigational site and be evaluated as soon as possible, preferably within 48 hours from awareness of the abnormal results. This evaluation should include laboratory tests, detailed history and physical assessment. The possibility of hepatic neoplasia (primary or secondary) should be considered. In addition to repeating measurements of AST and ALT, laboratory tests should include albumin, creatine kinase, total bilirubin, direct and indirect bilirubin, gamma-glutamyl transferase, prothrombin time (PT)/international normalized ratio (INR), ALP, and total bile acids and acetaminophen drug and/or protein adduct levels. A detailed history, including relevant information, such as review of ethanol, acetaminophen, recreational drug and supplement consumption, family history, occupational exposure, sexual history, travel history, history of contact with a jaundiced person, surgery, blood transfusion, history of liver or allergic disease, and work exposure, should be collected. Further testing for acute hepatitis A, B, or C infection and liver imaging (e.g., biliary tract) may be warranted. All cases confirmed on repeat testing as meeting the laboratory criteria defined above, with no other cause for LFT abnormalities identified at the time should be considered potential Hy's Law cases irrespective of availability of all the results of the investigations performed to determine etiology of the abnormal LFTs. Such potential Hy's Law cases should be reported as SAEs.

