5. At least 1 measurable target lesion according to Response Evaluation Criteria in Solid Tumors (RECIST) v1.1. Subjects with central nervous system (CNS)-only measurable target lesion ≥ 5 mm as defined by RECIST v1.1 are eligible.
6. Required wash-out time that is related to prior therapies before starting repotrectinib combination treatment:
 - At least 14 days or 5 half-lives (whichever is shorter) must have elapsed after discontinuation of prior systemic therapy and all side effects from prior treatments must have resolved to grade ≤ 1 with the exception of alopecia.
 - At least 14 days must have elapsed after discontinuation of prior immunotherapy and all immune-related side effects from prior immunotherapy must have resolved to grade ≤ 1 .
7. Subjects with asymptomatic CNS metastases (treated or untreated) and/or asymptomatic leptomeningeal carcinomatosis are eligible to enroll if they satisfy the following criteria:
 - Subjects requiring steroids at a stable or decreasing dose (≤ 12 mg/day dexamethasone or equivalent) for at least 14 days.
 - Subjects on stable doses of levetiracetam (same dose for 14 days).
 - A minimum of 14 days must have elapsed from the completion of whole brain radiation treatment (WBRT) before the start of treatment, and all side effects (with the exception of alopecia) from WBRT are resolved to grade ≤ 1 .
 - A minimum of 7 days must have elapsed from the completion of stereotactic radiosurgery before the start of treatment and all side effects (with the exception of alopecia) from stereotactic radiosurgery are resolved to grade ≤ 1 .
8. Baseline laboratory values fulfilling the following requirements:

Absolute Neutrophils Count	$\geq 1,500/\text{mm}^3 (1.5 \times 10^9/\text{L})$
Platelets	$\geq 100,000/\text{mm}^3 (100 \times 10^9/\text{L})$ independent of platelets transfusion support for at least 7 days prior to dosing
Hemoglobin	$\geq 9.0 \text{ g/dL}$ independent of transfusion support for at least 7 days prior to dosing
Creatinine Clearance*	$> 40 \text{ mL/min}$

Total Serum Bilirubin	< 1.5 x ULN ($\leq 3.0 \times$ ULN for patients with Gilbert's Syndrome or liver metastases)
Liver Transaminases (AST/ALT)	< 2.5 x ULN; < 5 x ULN if liver metastases are present
Alkaline Phosphatase	< 2.5 x ULN; < 5 x ULN if liver and/or bone metastasis are present.
Serum Calcium, Magnesium and Potassium	Normal or CTCAE grade ≤ 1 with or without supplementation.

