3.5.1. Dose Interruptions and Delays

Dose interruptions may occur in the event of a treatment-related toxicity or a non-treatment-related issue (e.g., elective surgery). If toxicity is clearly attributed to one drug based on the known toxicity profile then one drug may be interrupted while the other is continued. If the toxicity cannot clearly be attributed to one drug, then dose interruption for both drugs will be implemented.

Appropriate follow-up assessments should be done until adequate recovery occurs as assessed by the Investigator. Criteria required before treatment can resume for repotrectinib are described in the dose modification guidelines for adverse events table ([Table 4](#)). The guidelines provided in [Table 4](#) are general guidelines for dose modifications due to toxicities that may arise from repotrectinib. The guidelines provided in the label for trametinib should be referenced and followed to manage toxicities (i.e., see Table 2 in [Mekinist® \[trametinib\] USPI 2020](#)).

Doses may be held as needed until toxicity resolution. Depending on when the AE is resolved, a treatment interruption may lead to the subject missing all subsequent planned doses within that same cycle or even to delay the initiation of the subsequent cycle.

If a treatment delay results from worsening of hematologic or biochemical parameters, the frequency of relevant laboratory assessments may be increased as clinically indicated.

If the AE that led to the treatment interruption recovers within the same cycle, then re-dosing in that cycle is allowed. Doses omitted for toxicity are not replaced within the same cycle. The need for a dose reduction at the time of treatment resumption should be based on the criteria defined in [Table 4](#) unless otherwise agreed to following discussion between the Investigator and the Medical Monitor.

In the event of a treatment interruption for reasons other than treatment-related toxicity (e.g., elective surgery) lasting \geq 14 days, treatment resumption must be discussed with the Medical Monitor.

All study visits (visit date calculations) are based off the Cycle 1 Day 1 visit date, regardless of dose interruptions, and evaluations are to be performed according to the Schedule of Activities ([Table 1](#)). Every effort should be made to maintain the tumor assessments scheduling as described in the Schedule of Activities.

Table 4: Repotrectinib Dose Modification Guidelines for Adverse Events (CTCAE v5.0)

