AST or ALT elevation	Continue at same dose level.	Continue at same dose level. Withhold current dose if concurrent CTCAE grade ≥ 2 total bilirubin elevation ($> 1.5 \times$ ULN).	Withhold current dose until resolves to Grade ≤ 1 .	Discontinue treatment permanently.
Prolonged QTc	Assess electrolytes and concomitant medications. Correct any electrolyte abnormalities, or hypoxia. Continue at the same dose level.	Assess electrolytes and concomitant medications. Correct any electrolyte abnormalities, or hypoxia. Continue at the same dose level.	Withhold dose Assess electrolytes and concomitant medications. Correct any electrolyte abnormalities, or hypoxia. Upon recovery to grade ≤ 1 : if no other cause for QTc prolongation is found or is considered drug-related resume treatment at 1 dose level lower.	Discontinue treatment.
Dizziness, ataxia, or muscular weakness	Continue at same dose level.	Withhold current dose until toxicity is grade ≤ 1 or has returned to baseline OR reduce by 1 dose level immediately ^{1,2}	Withhold dose until toxicity is grade ≤ 1 or has returned to baseline, then reduce by 1 dose level ^{1,2} and resume treatment	Withhold dose until toxicity is grade ≤ 1 or has returned to baseline, then reduce by 1 dose level ^{1,2} and resume treatment; or discontinue treatment as per the Investigator's discretion after discussion with Medical Monitor.

Toxicity	CTCAE Grade 1*	CTCAE Grade 2*	CTCAE Grade 3	CTCAE Grade 4
Weight gain	Continue at same dose level. Implement effective weight management strategy (dietary advice from a nutritionist and food intake counseling).	Dose interrupt or dose reduce ^{1,2} , if required.	Dose interrupt or dose reduce ^{1,2} , if required.	Not applicable.

Abbreviations: ALT = alanine aminotransferase; AST = aspartate aminotransferase; CNS = central nervous system; CTCAE = Common Terminology Criteria for Adverse Events, v5.0; ILD = interstitial lung disease; QTc = QT interval corrected for heart rate; ULN = upper limit of normal.

*Cycle will not be extended to cover for the missing doses. In cases where no specific dose adjustments for CTCAE Grade 1 or Grade 2 treatment-related toxicity are provided, Investigators should always manage their subjects according to their medical judgment, which may include dose reduction or interruption based on the particular clinical circumstances.

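### Section 8.2.5.6 keeps a fixed ALP limit in the potential Hy's Law definition, so a subject who enters with ALP above 2 × ULN and stays there may never be flagged (minor; safety reporting only)

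*Combined protocol and SAP*

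**What the plan says.** Section 8.2.5.6 sets out a principle before it gives any limits: "The threshold of laboratory abnormalities for a potential case of drug-induced liver injury depends on the subject's individual baseline values and underlying conditions". It then has two bullets.

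- Subjects with normal baseline AST/ALT and total bilirubin are flagged at AST or ALT above 3 × ULN with bilirubin above 2 × ULN, "with no evidence of hemolysis and an ALP value $\leq 2 \times$ ULN or not available".
- Subjects with raised baseline ALT, AST or bilirubin get replacement limits within the same definition. For AST/ALT: at least twice baseline and at least 3 × ULN, or at least 8 × ULN, whichever is smaller. For bilirubin: a rise of at least 1 × ULN, or a value of at least 3 × ULN, whichever is smaller. ALP has no replacement limit, and a raised baseline ALP does not bring a subject into this bullet.

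The entry limit for ALP (Section 4.1, criterion 8, and the Synopsis) is "< 2.5 x ULN; < 5 x ULN if liver and/or bone metastasis are present".

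Meeting the laboratory limits leads to an evaluation "preferably within 48 hours from awareness of the abnormal results" with a listed set of tests. The reporting step covers "All cases confirmed on repeat testing as meeting the laboratory criteria defined above", provided no other cause has been identified. It ends: "Such potential Hy's Law cases should be reported as SAEs". SAEs must be reported within 24 hours (Sections 8.1.1 and 8.3).

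**The concern.** The protocol accepts metastatic disease as a reason for raised ALP at entry, but the liver-injury rule takes no account of that baseline. The ALP clause has a purpose: a raised ALP can point to cholestasis, which Section 8.2.5.4 uses as an example. An ALP that has not moved since entry is not by itself evidence of new cholestasis. For such a subject the clause removes a possible hepatocellular signal for a reason that was present before the first dose. At stake is whether a possible drug-induced liver injury receives the prescribed work-up and is reported by rule.

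**Working it through.** This is a check of the rule's logic; the plan gives no figure to reproduce. All values are multiples of ULN.

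**Rule as written, first bullet.** Flag if (AST or ALT > 3) and (bilirubin > 2) and no hemolysis and (ALP ≤ 2 or not available).

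**Eligible entry ALP that fails the clause while unchanged.** Above 2 and below 2.5 without liver or bone metastases; above 2 and below 5 with them. ALP is in the same chemistry panel as AST, ALT and bilirubin (Section 6.11, Table 7), so it would rarely be unavailable.

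**Illustrative records (assumed values).** AST/ALT and bilirubin are normal at entry and there is no hemolysis. At the event AST is 4 and bilirubin 2.5, so both limits are met and only ALP decides. The last column accepts ALP up to 1.25 × baseline when baseline ALP exceeds 2: 1.25 × 3.0 = 3.75 and 1.25 × 2.4 = 3.00.

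| Entry ALP | Event ALP | Flagged as written | Flagged with margin |
|---|---|---|---|
| 3.0 | 3.0 | no | yes |
| 3.0 | 3.1 | no | yes |
| 2.4 (no metastases) | 2.4 | no | yes |
| 3.0 | 1.8 | yes | yes |
| 3.0 | not available | yes | yes |
| 3.0 | 4.5 (risen) | no | no |
| 1.0 | 2.5 (newly raised) | no | no |

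As written, an unknown ALP keeps the case in and an unchanged ALP of 3.0 takes it out. The added condition changes only the three records with an essentially stable ALP.

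**Why a margin is needed.** Suppose true ALP is constant and the baseline, event and repeat readings are exchangeable and continuous. A rule of no rise above baseline at both event and repeat requires the baseline to be the highest of three readings: probability 1/3. About 1 − 1/3 = 2/3 of unchanged-ALP subjects would then go unconfirmed. The factor 1.25 is an assumption. In the table, 3.1/3.0 = 1.03 and 4.5/3.0 = 1.5, so any factor from 1.04 to 1.49 classifies these records in the same way.

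**Subjects with raised baseline AST/ALT or bilirubin.** The second bullet substitutes limits into the definition above it, which suggests that the ALP clause carries over. Its sub-bullets restate only AST/ALT and bilirubin, so one can also read the clause as binding the first bullet alone. The text leaves this open. A subject whose only raised baseline test is ALP stays in the first bullet on either reading.

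**What still operates without an ALP condition.**

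- Table 4, grade 2 AST/ALT: "Withhold current dose if concurrent CTCAE grade" 2 or higher bilirubin is present (above 1.5 × ULN). That is a lower bilirubin limit than 2 × ULN, so the hold does not come later than the flag would.
- Table 4 also withholds at grade 3 AST/ALT and discontinues permanently at grade 4.
- Section 3.5.1 interrupts both drugs if attribution is unclear, and adds: "Appropriate follow-up assessments should be done until adequate recovery occurs as assessed by the Investigator".
- A result that changes treatment is a reportable AE (Section 8.2.5.4), with seriousness and causality assessed (8.2, 8.2.4) and follow-up to resolution or stability (8.4.1).
- Grade 4 and 5 events are SAEs (Section 8.2.3, Table 8, footnote d), as are AEs requiring hospitalization, with listed exceptions (8.1.1, 8.2.5.10).
- In Phase 1b Cycle 1, bilirubin above 1.5 × ULN with AST or ALT above 3 × ULN is a DLT (Table 3).

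**What none of these supplies.** Besides repeat AST/ALT, the work-up lists nine items. Four are routine (albumin, total bilirubin, ALP, PT/INR), leaving 9 − 4 = 5 outside the Table 7 panels: creatine kinase, direct and indirect bilirubin, gamma-glutamyl transferase, total bile acids, and acetaminophen levels.

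**The case against.** The strongest reply is that little is lost. Treatment is held or stopped whatever the ALP, grade 4 events and hospitalizations are SAEs by rule, and Section 8.6 lets the sponsor upgrade seriousness when deciding regulatory reports. The wider entry range applies only to subjects with liver or bone metastases, and where liver metastases explain the results the no-other-cause condition would rule out a Hy's Law case anyway. Without metastases the window is only 2 to 2.5 × ULN. Almost all of this stands, and it is why the point is minor. Table 8 is introduced for AEs that CTCAE does not list, but the wording of footnote d is not restricted to them, and I take it at face value.

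The reply does not close the gap. None of these provisions prescribes the Hy's Law work-up or the prompt evaluation, and the DLT rule does not reach later cycles or Phase 2. The no-other-cause condition is applied after evaluation, whereas the ALP clause prevents the evaluation from being triggered.

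A fair criticism of the remedy is that a cut at baseline ALP 2 × ULN leaves an edge: entry 1.9 rising to 2.1 is still excluded, while 2.4 unchanged is included. That edge is the price of leaving the existing limit alone for everyone else.

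**Conclusion.** The point holds as a minor defect in a safety-reporting definition. A subject with normal baseline AST/ALT and bilirubin, and with ALP above 2 × ULN at entry and at the event, cannot be flagged. Subjects with raised baseline AST/ALT or bilirubin are affected too if the ALP clause carries into the second bullet. The loss is the prescribed work-up, the prompt evaluation, and the automatic SAE report for non-hospitalized cases below grade 4 that meet no other fixed SAE criterion. For those cases SAE reporting rests on the investigator's view that the event is medically significant.

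A reader might infer that such a subject would go unmanaged, or that every such SAE report depends on the investigator's judgment. The documents support neither, given the Table 4 actions and the fixed SAE criteria. Nor do they support a claim that all subjects with raised baseline liver tests are certainly excluded, since the second bullet has two readings.

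The number affected cannot be computed: the documents give neither the distribution of entry ALP nor the rate of combined AST/ALT and bilirubin elevations. It is probably small. No endpoint, estimate, sample size or stopping rule changes.

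**What to change.** Add one bullet to Section 8.2.5.6, for example: *For subjects with baseline ALP > 2 × ULN, the ALP condition is met if ALP has not risen above baseline by more than a prespecified margin for assay variation (e.g. ALP ≤ 1.25 × baseline), or is not available.* The 1.25 is for the sponsor to confirm. Apply the bullet at first presentation and at repeat testing, with the same baseline as for AST/ALT and bilirubin, and leave the no-other-cause condition as it is. A few words should also settle whether the ALP clause applies to the second bullet.

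No new visit or routine test is needed, because ALP is already in the chemistry panel at Screening and on Cycle 1 Day 1 (optional if done within the past 7 days). The cost is a few extra work-ups, some of which metastases will explain.

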8.2.5.7. Deaths

Death due to disease progression will not be reportable as an SAE. The immediate cause of death will be the serious reported term.

All deaths, regardless of relationship to study drug, must be recorded on the Death CRF and on the Adverse Event CRF if considered an AE and occurred within the 28-day AE reporting window. Deaths reported as "disease progression" are not to be reported as SAEs if they occur within the 28-day window.

Death should be considered an outcome and not a distinct event. The event or condition that caused or contributed to the fatal outcome should be recorded as the single medical concept on the Adverse Event CRF. Generally, only one such event should be reported. The term "**sudden death**" should be used only for the occurrence of an abrupt and unexpected death due to presumed cardiac causes in a subject with or without preexisting heart disease, within 1 hour after the onset of acute symptoms or, in the case of an unwitnessed death, within 24 hours after the subject was last seen alive and stable. If the cause of death is unknown and cannot be ascertained at the time of reporting, "unexplained death" should be recorded on the Adverse Event CRF. If the cause of death later becomes available (e.g., after autopsy), "**unexplained death**" should be replaced by the established cause of death.

